#### Control product

The control procedure is endoscopy. Endoscopes and associated devices and accessories are chosen as per site protocol, physician's discretion and provided by NYU.

#### **6.1.2 Formulation, Appearance, Packaging, and Labeling**

##### Subject device

HemoPill acute capsules are provided sterile in a transport carton containing single blister packaging and instructions for use. The HemoPill Receiver is provided non-sterile in a transport carton containing blister packaging and instructions for use. The subject device is provided by Ovesco USA Inc. Ovesco Endoscopy AG is the legal manufacturer of the subject device for the European market. For trial purposes, the subject device is to be considered as an investigational device. The subject device is available for human use in the EU and does not require alterations to meet the trial plan.

#### Control product

The control procedure is endoscopy. Endoscopes and associated devices and accessories are chosen as per site protocol, physician's discretion and provided by NYU.

#### **6.1.3 Product Storage and Stability**

##### Subject device

The HemoPill acute capsules are provided sterile in single blister packaging. As marketed devices, sterilization validation, transport simulation, aging etc. has been conducted. The sterile HemoPill acute capsule has a shelf life of two years. Information on storage conditions is provided on device labeling and used visuals are described in the instructions for use. The HemoPill acute capsules should be stored between 10°C and 30°C and protected from direct solar radiation. Relative humidity during storage should be between 20 % and 85 %, non-condensing.

The HemoPill Receiver is provided non-sterile. It has a service life of 10 years. Storage conditions should be:

- Temperature: between – 10°C and + 50°C
- Relative humidity: 20 % to 90 %, non-condensing
- Air pressure: 700 to 1,060 hPa

While storage temperatures may be as low as – 10°C, the HemoPill Receiver needs to acclimatize to room temperature is stored below + 10°C. Further information is provided in the instructions for use.

#### Control product

The control procedure is endoscopy. Endoscopes and associated devices and accessories are chosen as per site protocol, physician's discretion and provided by NYU. Respective storage conditions apply as indicated on the device labeling.

#### **6.1.4 Preparation**

##### Subject device

In the following the stepwise clinical use of the HemoPill acute is described

- Switching on the HemoPill Receiver
- Activation of the HemoPill acute using the HemoPill Receiver
- Establishment of a data connection between HemoPill acute and HemoPill Receiver
- Handing the activated HemoPill acute to the patient in the blister
- Swallowing of the HemoPill acute with a small amount of water

- Receiving and reading of measurement data (HI values) using the HemoPill Receiver
- Interpretation of the measured values by the user based on the information provided in the IFUs of the HemoPill acute and HemoPill Receiver (document A01)
- At the end of measurement, deactivation of the data connection with the HemoPill Receiver
- Natural excretion of the HemoPill acute by the patient

A detailed description on the handling of the HemoPill Receiver can be found in the respective instructions for use, provided as a separate document.

Control product

The control procedure is endoscopy. Endoscopes and associated devices and accessories are chosen as per site protocol, physician's discretion and provided by NYU. Use of endoscopy is clinically established, as are requirements for preparation.

**6.1.5 Dosing and Administration**

Subject device

The HemoPill acute capsule is switched on using the HemoPill Receiver as described in the instructions for use. A data connection between the HemoPill acute capsule and the HemoPill Receiver is established. Every trial participant receives a single, sterile, switched on HemoPill acute capsule for ingestion with a minimal amount of water. The HemoPill acute capsule is not to be chewed. Ingestions is timed under consideration of endoscopy scheduling. Minimum latency to endoscopy should be 20 minutes, maximum latency to endoscopy should be one hour. The HemoPill Receiver is operated by the investigators.

Control product

Application of endoscopy as per clinical standard. Scheduling of endoscopy follows NYU protocol and suspected urgency of a given patient's situation.

**6.1.6 Route of Administration**

Subject device

Administered orally by ingestion.

Control device

Oral introduction of endoscope.

**6.1.7 Starting Dose and Dose Escalation Schedule**

Not applicable.

**6.1.8 Dose Adjustments/Modifications/Delays**

Not applicable.

**6.1.9 Duration of Therapy**

From HemoPill acute capsule ingestion to start of endoscopy, a maximum of 60 minutes elapse. Duration of endoscopy depends on presence or absence of pathologies and time needed for treating pathologies if found.

### 6.1.10 Tracking of Dose

Not applicable.

### 6.1.11 Device Specific Considerations

#### Subject device

- Device size:
  - Length: 26.3 mm
  - Maximum diameter: 7 mm
  - Weight: 2 g
- Device model
  - HemoPill acute capsule: Software version 02.xx.yy
  - HemoPill Receiver: Software version 02.xx.yy
- Device settings and programming
  - HemoPill acute capsule: No settings or adjustments can be made during the trial. Software version 02.02.xx is implemented.
  - HemoPill Receiver: The HemoPill Receiver is used for activating a HemoPill acute capsule, for establishing a data connection between a HemoPill acute capsule and for displaying HemoPill acute measurements. Up to 50 data sets can be stored on the HemoPill Receiver. The HemoPill Receiver can be used to display, store, and delete data sets. The HemoPill Receiver cannot be used to alter or manipulate data sets.
- Frequency of exposure
  - HemoPill acute capsule: Once, duration of exposure from ingestion to excretion
  - HemoPill Receiver: Once, from establishing a data connection to a HemoPill acute capsule to conclusion of the measurement.

### 6.2 Study Agent Accountability Procedures

The subject devices are provided to NYU by Ovesco. Distribution of HemoPill acute capsule is within the responsibility of the investigators. For trial purposes, at least 50 HemoPill acute capsules and minimum 2 HemoPill Receivers will be provided to NYU. Requirements for adequate and safe handling are provided by described storage conditions. Unused products are returned to Ovesco Endoscopy AG.

### 6.3 Study Procedural Intervention(s) Description

Within the scope of the proposed trial, HemoPill acute capacity for providing information on the presence or absence of blood in the GI lumen is controlled by relation to an endoscopic intervention. Latency to endoscopy is controlled. The trial procedure HemoPill acute introduces ingestion of the HemoPill acute capsule by the patient as a procedural intervention. Endoscopy however is not a procedural intervention in the sense that a patient is subjected to endoscopy for trial purposes. Endoscopy is already scheduled for the trial participant to further investigate the suspicion of UGIB and for treatment of lesions if identified.

#### 6.3.1 Administration of Procedural Intervention

The investigator activates the HemoPill acute capsule by using the HemoPill Receiver. A data connection to the HemoPill Receiver is established. The activated HemoPill acute, still within the blister, is handed to the trial participant for ingestion with a minimal amount of water. Ingestion is timed under consideration of the previously established scheduling for endoscopy. Between HemoPill acute ingestion and start of

endoscopy, a minimum of 20 minutes should have elapsed. No more than 60 minutes between HemoPill acute ingestion and start of endoscopy should elapse. A trial participant is subjected to one intervention.

### **6.3.2 Procedures for Training of Clinicians on Procedural Intervention**

Investigators are trained in the use of the HemoPill acute capsule and HemoPill Receiver. Adequate training material is available. As the subject device is already marketed in the EU, usability data and user feedback are available, indicating a safe and easy use. For endoscopy, no additional training is provided. Investigators are however instructed to document finding of blood and/or hematin in the GI lumen if identified. A single investigator trained for estimating amounts of blood and/or hematin on the basis of endoscopic images will assess the amount of blood/hematin found. He or she will be provided reference images. He or she will be unaware of respective HemoPill acute measurements.

### **6.3.3 Assessment of Clinician and/or Participant Compliance with Study Procedural Intervention**

Not applicable.

## **7 Study Procedures and Schedule**

### **7.1 Study Procedures/Evaluations**

#### **7.1.1 Study Specific Procedures**

Trial specific procedures are only related to the use of the HemoPill acute. With relevance to the patient is HemoPill acute capsule ingestion. While endoscopy is performed as per clinical standard, additionally, images of blood or hematin are taken.

Only patients scheduled for endoscopy for suspicion of UGIB are eligible for trial participation. Suspicion of UGIB is established as per site protocol and/or physician's preference. After suspicion of UGIB is established and endoscopy scheduled, eligible patients are approached. Adequate patient information is provided. Only if informed consent is acquired, inclusion criteria are met and no exclusion criteria apply, may a patient enter into the trial as a trial participant.

#### **7.1.2 Standard of Care Study Procedures**

Standard of care procedures are:

- Clinical and laboratory evaluations as per standard of care, including but not limited to, complete blood count, and initial consultation
- Endoscopy: As a diagnostic as well as curative tool for UGIBs, endoscopy is applied in all patients to investigate a suspicion of UGIB. If a pathology is found, it is treated as per clinical standard. If blood or hematin are found, images are taken for later volume evaluation.

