**Protocol Summary**

Title	Presence or Absence of blood in the GI lumen – Relation between a HemoPill acute measurement with a subsequent endoscopic finding
Short Title	PROOF (Presence or Absence of blood in the GI lumen – Relation between a HemoPill acute measurement with a subsequent endoscopic finding)
Brief Summary	Patients scheduled for endoscopy on the basis of suspected UGIB are generally eligible for inclusion into the trial. After patient screening, information and obtaining informed consent, a patient is enrolled into the trial. Shortly before the scheduled endoscopy is performed, the patient ingests a HemoPill acute. Endoscopy is performed as scheduled. Blood within the GI lumen is identified if present and pictures are taken. Pathologies, if found, are treated as per clinical standard. The HemoPill acute measurement regarding presence or absence of blood in the GI lumen is compared to observations made during endoscopy. For statistical validity, 43 patients are required. Considering dropouts, a recruitment goal of 50 patients is defined.
Phase	N.A.
Objectives	The objective of the study is to determine the clinical relation between the detection of blood in the GI lumen using the HemoPill acute (trial procedure) with the detection of bleeding / a bleeding source during an endoscopic examination (control procedure).
Methodology	Intraindividual comparison of HemoPill acute measurement to endoscopic work up.

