## 4 Study Design and Endpoints

### 4.1 Description of Study Design

Patients are included according to the defined inclusion criteria and prepared for endoscopy. At the latest possible time before endoscopy, a HemoPill acute capsule is administered with a minimal amount of water. The HemoPill receiver is stored in a carrying bag. The transparent part of the bag over the display of the receiver is covered with tape. The LED light is left uncovered, so a successful signal transmission can be checked at any times. The investigator is unaware of the HemoPill acute measurement result until endoscopy has concluded. After a latency of minimum 20 minutes, maximum 60 minutes, endoscopy is performed as scheduled, identifying blood within the GI lumen, if present. A minimum latency is introduced to ensure HemoPill acute is able to make a measurement without interference from endoscopy, e.g., insufflation or endoscopic light.

The amount of blood identified in endoscopy is visually analyzed and pictures are taken. For the estimation of the amount of blood present in a patient, comparative images are provided. Assessment categories are:  $x < 20$  mL and  $x > 20$  mL. The detection threshold is introduced to provide a point of reference for the HemoPill acute detection rate.

Pathologies, if found, are treated as per clinical standard. HemoPill acute measurements regarding presence or absence of blood are put in relation to endoscopic findings.

Endoscopic images are further analyzed to determine the digestive state of the blood found as HemoPill acute is capable of detecting fresh blood or hematin. Blood digested to a point beyond hematin is no indicator for an acute bleeding pathology. The following foreseeable combination of events are described and allocated to “True Positive”, “False Positive”, “True Negative”, and “False Negative”.

- **True positive:**  
HemoPill acute measurement indicates presence of blood; Endoscopy identifies fresh blood or hematin in the GI lumen
- **False positive:**  
HemoPill acute measurement indicates presence of blood; Endoscopy does not identify fresh blood or hematin in the GI lumen.
- **True negative:**  
HemoPill acute measurement does not indicate presence of blood; Endoscopy does not identify fresh blood or hematin in the GI lumen in quantities  $> 20$  mL; Minimum latency of 20 minutes achieved.
- **False negative:**  

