## 10.6 Measures to Minimize Bias

### 10.6.1 Enrollment/Randomization/Masking Procedures

While the study is an intra-individual relation between a HemoPill acute measurement and an endoscopic examination and thus not randomized, masking is achieved by application of the following considerations:

- Patient: Sedated during endoscopy. Does not know how to interpret information displayed by the HemoPill Receiver. He or she does not provide an interpretation of measurements.
- Endoscopist: While aware of the endoscopic presentation of the patient as it unfolds, the investigator is unaware of the HemoPill acute measurement. The relation between the HemoPill acute measurement and endoscopic findings is investigated after endoscopy has concluded.
- Blood quantification: A third person quantifies the amount of blood depicted on endoscopic images. This person is unaware of the respective HemoPill acute measurement. A relation to the HemoPill acute measurement is made only after the quantification of blood depicted has been made.

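### Images are specified only when the endoscopist has found blood or hematin, so examinations called negative get no masked second read and a missed finding cannot be corrected

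*Combined protocol and SAP*

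**What the plan says.** Three sections tie images or documentation to a positive finding:

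- 7.1.2: "If blood or hematin are found, images are taken for later volume evaluation".
- 7.1.1: endoscopy follows clinical standard and "additionally, images of blood or hematin are taken".
- 6.3.2: "Investigators are however instructed to document finding of blood and/or hematin in the GI lumen if identified".

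Two places are looser. The Protocol Summary says "Blood within the GI lumen is identified if present and pictures are taken", and 4.1 says "The amount of blood identified in endoscopy is visually analyzed and pictures are taken". Both sentences concern blood that was seen, and neither states what happens when none is seen.

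On the later assessment, 6.3.2 says "A single investigator trained for estimating amounts of blood and/or hematin on the basis of endoscopic images will assess the amount of blood/hematin found", and 10.6.1 says "A third person quantifies the amount of blood depicted on endoscopic images". Both sections keep this person unaware of the capsule result. Section 4.1 adds: "Endoscopic images are further analyzed to determine the digestive state of the blood found". It does not name who does this, and it treats blood digested past the hematin stage as no sign of an acute bleed.

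In 4.1 the 20 mL limit appears only in the true-negative and false-negative definitions. A true positive needs any fresh blood or hematin. Section 10.4.2 has the investigator turn the endoscopy into a positive or negative result and does not mention the image reader.

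**The concern.** Endoscopy is the reference standard for the primary endpoint, and it is assessed differently depending on its own first result. A called positive yields images that are looked at again. A called negative yields nothing that the plan requires anyone to look at again. Telling hematin from residue past that stage is assigned in 4.1 to image analysis, yet residue the endoscopist dismisses as neither blood nor hematin never reaches that analysis.

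The unreviewed group is where the plan expects its errors. Section 10.5 assumes sensitivity of 100% and specificity of 63%, so every expected error is a false positive: a positive capsule with nothing found at endoscopy. The protocol also names a rival explanation for such results. According to 2.1.2.2, undiluted bile can give an HI of about 1.0, which is the positive threshold after 10 minutes in Table 4 of 2.1.3. Without images, a bile artefact cannot be told from hematin that was overlooked.

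A smaller gap is that no section says when images are taken relative to suction, irrigation or treatment, although volume is judged from them.

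**Working it through.** **Step 1. What a second look can change, by capsule result (definitions in 4.1).**

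| Capsule | Blood missed or dismissed at the bedside | Blood found and imaged |
|---|---|---|
| Positive | Counted as false positive; no required image | Volume category has no effect; a judgement of digested past hematin would remove the positive |
| Negative | Counted as true negative, wrongly if above 20 mL; no required image | Volume category decides between true and false negative, in either direction; digestive state can also remove a positive |

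The left column has no planned correction and the right column has some. The right column is not purely a downgrade, since a reading above 20 mL in a capsule-negative patient creates a false negative.

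**Step 2. The plan's own accuracy.** Section 2.1 reports 60 analysed patients in the cited multicentre series: 35 capsule-positive, 20 of them with bleeding confirmed, and 25 capsule-negative, none with bleeding found. Counting as 10.5 does:

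- accuracy = (20 + 25)/60 = 75%
- sensitivity = 20/20 = 100%
- specificity = 25/(25 + 15) = 62.5%, stated as 63%
- share with confirmed bleeding = 20/60 = 1/3

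The stated figures are reproduced.

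**Step 3. Effect of uncorrected misses.** Inputs are prevalence p = 1/3 (assumed, from step 2), sensitivity 1 and specificity 0.63 (10.5), and a miss rate m, which is assumed because the documents give none. Misses are taken as independent of the capsule because the endoscopist is masked to it (4.1).

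- Accuracy = p(1 − m) + (1 − p)(0.63) = (1 − m)/3 + 0.42
- Specificity = 0.42/(0.6667 + m/3)

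| Assumed miss rate | Accuracy | Specificity | Missed, of 43 × 1/3 = 14.3 |
|---|---|---|---|
| 0% | 75.3% | 63.0% | 0 |
| 5% | 73.7% | 61.5% | 0.7 |
| 10% | 72.0% | 60.0% | 1.4 |
| 20% | 68.7% | 57.3% | 2.9 |

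Apparent sensitivity stays at 100%. One reclassified patient is 1/43 = 2.3 points of accuracy.

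**Step 4. The other direction.** Suppose instead that an assumed 5% or 10% of truly negative examinations are over-called and survive the read. Sensitivity falls to 94.3% or 89.5% and accuracy to 74.5% or 73.6%, with specificity unchanged at 63%. Both error directions exist, and they damage different indices.

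**Step 5. If capsule sensitivity is below 100%.** With an assumed sensitivity of 80%, and missed blood in capsule-negative patients taken to be above 20 mL, some misses turn false negatives into true negatives and offset part of the loss. Accuracy goes from 68.7% to 67.7%, 66.7% and 64.7% at the same three miss rates. The net effect is still downward.

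**The case against.** Four points can be made for the plan.

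First, the endoscopist does not know the capsule result, so misses should not follow it. That stands and rules out one source of bias, but masking does not recover a missed finding.

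Second, nothing forbids images in a negative examination, the Protocol Summary and 4.1 can be read either way, and section 9 makes the procedure report available for verification. This stands as far as it goes: the gap is a missing requirement, not a prohibition. The report is the endoscopist's own account and does not replace a masked read.

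Third, a reader might infer that the reference standard can err in one direction only. The documents do not support this. An endoscopist's over-call can be accepted on review, and a single reader estimating volume by eye can overestimate it or misjudge digestive state. A finding judged merely small should still be imaged under 7.1.2, so only findings missed or judged not to be blood or hematin are lost.

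Fourth, a reader might take the expected false positives, 0.25 × 43 = 10.75 or about 11 patients, as the size of the problem. That is a count of expected false positives, not of reference errors. In the cited series only 11 of the 15 unconfirmed positives had an EGD (2.1), and scaling those gives 11/60 × 43 = 7.9, about 8. That series also included suspected small-bowel bleeding, and its median time to EGD in capsule-positive patients was 3 h 18 min (2.4.2), against 20 to 60 minutes here. Location and delay may explain many of those results.

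**Conclusion.** The point holds in limited form. Examinations called negative have no required images and no masked second read, so blood or hematin missed or dismissed at the bedside cannot be corrected, while called positives are reviewed. The imbalance is in the opportunity to correct.

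Under the plan's own assumptions the main effect runs against the device: missed blood occurs in capsule-positive patients and lowers specificity and accuracy. The path that favours the device, missed blood above 20 mL with a negative capsule, has an expected count of zero at 100% sensitivity and appears only if sensitivity is lower.

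The size is a loss of about 2 to 7 accuracy points (75.3% to between 73.7% and 68.7%). It rests on assumed miss rates of 5% to 20%, a prevalence of 1/3 and misses independent of the capsule. The true miss rate is unknown and, without images in negative examinations, could not be assessed by a masked image read. It is also unsettled whether the reader's judgement overrides the investigator's under 10.4.2.

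**What to change.** In 7.1.1, 7.1.2 and 6.3.2, require the same short set of stills in every participant, with or without visible blood, taken on first view where this does not delay or alter clinical care. Give all sets in mixed order to the masked reader already planned, who classifies presence, digestive state and volume category for each. In 10.4.2, state whether the reader's or the endoscopist's call is final.

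The cost is a few extra stills during an endoscopy already under way and up to 50 sets to read, with no new staff or procedure. The wording must stay consistent with the commitment in 2.1.1 and 2.4.1 that the study does not hold up or lengthen endoscopy, so a set that cannot be completed should be recorded as incomplete, not pursued. Images not taken during the examination cannot be obtained afterwards, so the change is useful only for participants enrolled after it takes effect.
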